5.5 Concomitant Medications

All medications (prescription and over-the-counter), vitamin and mineral supplements, and/or herbs taken by the participant will be documented on the concomitant medication CRF and will include: 1) start and

stop date, dose and route of administration, and indication. Medications taken for a procedure (e.g., biopsy) should also be included.

5.6 Dose Modification

No dose modifications are planned. The study agent will be stopped in the event of an AE \geq grade 3 considered possibly, probably, or definitely related to the study agent. The study agent will be restarted after resolution. One of the common side effects of statin medication is myalgia (muscle pain with normal creatine phosphokinase (CPK) level), and rarely this is associated with statin myopathy (muscle weakness or other muscle injury with or without elevation in CPK level). In randomized controlled trials of standard dose statin therapy, the risk is very low (<1%). We will measure levels of CPK in the blood drawn at the first study visit to establish a patient-specific reference for this indicator of muscle toxicity. During the trial, if the participant reports unexplained muscle pain or weakness, CPK will be tested again to check for elevation. The study agent will be temporarily discontinued in subjects experiencing grade 1 or greater myopathy (unexplained muscle symptoms *and* creatine phosphokinase (CPK) > 2.5 times institutional ULN) or hepatotoxicity (ALT or AST > 1.5 times institutional ULN) that is considered possibly, probably, or definitely related to the study agent. Resolution of myopathy or hepatotoxicity will be evaluated with follow-up laboratory blood tests 4 weeks after the elevated levels occur. If the lab test results are still elevated after 4 weeks, the study agent will be discontinued permanently and the participant's primary care physician will be notified of the abnormal tests. If the lab test results return to normal levels, participant will go back on the study agent.

Because dose modification could lead to lack of dose homogeneity that may impair the research objectives, we will stop the intervention in patients who initiate drugs that require dose modifications of simvastatin below 40 mg: lomitapide, verapamil, diltiazem, dronedarone, amiodarone, amlodipine, or ranolazine.

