4.2.2 History of chronic myopathy

4.2.3 Current use of any other investigational agents

- 4.2.4 History of adverse effects, intolerance, or allergic reactions attributed to compounds of similar chemical or biologic composition to simvastatin (i.e., other statin medications).
- 4.2.5 Uncontrolled intercurrent illness including, but not limited to, ongoing or active infection, symptomatic congestive heart failure, unstable angina pectoris, cardiac arrhythmia, or psychiatric illness/social situations that would limit compliance with study requirements.
- 4.2.6 Women who are pregnant or breastfeeding. Pregnant women are excluded from this study because simvastatin is a lipid-lowering agent with the potential for teratogenic or abortifacient effects. Because there is an unknown but potential risk for adverse events in nursing infants secondary to treatment of the mother with simvastatin, breastfeeding should be discontinued if the mother is treated with simvastatin.
- 4.2.7 Presence of gallstones or hypertriglyceridemia (level greater than 800 mg/dl) that requires medical or surgical intervention. *Note: We will include patients who had an independent episode of pancreatitis after a cholecystectomy, but exclude patients who are candidates for cholecystectomy.*
- 4.2.8 History of pancreatic adenocarcinoma (at any time)
- 4.2.9 History of active malignancy in the past 2 years (excluding basal/squamous cell skin cancer or prostate cancer with a Gleason score 6 or less)
- 4.2.10 Known active infection with HIV
- 4.2.11 Concurrent illness, such as known psychiatric disorders or substance abuse (i.e., average alcohol consumption of more than 5 drinks per day), which in the opinion of the investigators would compromise either the patient or the integrity of the data
- 4.2.12 Lab results do not meet inclusion criteria 4.1.4 by Screen 2.
- 4.2.13 Recurrent pancreatitis episode is iatrogenic (endoscopic retrograde cholangiopancreatography (ERCP) induced)
- 4.2.14 Advanced chronic pancreatitis as determined by the following criteria: EUS score greater than or equal to 6, calcifications in combination with atrophy and/or dilation of ≥ 5 mm, or evidence of advanced chronic pancreatitis by computed tomography (CT) or magnetic resonance imaging (MRI) results in the past 12 months.

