6.2 Reported Adverse Events and Potential Risks

The most common (incidence $\geq 5.0\%$ patients) reported adverse events (AEs) are upper respiratory infection, headache, abdominal pain, constipation, and nausea. Other AEs reported in clinical trials ($<5\%$) were diarrhea, rash, dyspepsia, flatulence, and asthenia.

Persistent increases in serum transaminases (to more than 3 x ULN) have occurred in approximately 1% of patients who received simvastatin in clinical studies. When drug treatment was interrupted or discontinued in these patients, the transaminase levels usually fell slowly to pretreatment levels. The increases were not associated with jaundice or other clinical signs or symptoms. It is recommended that liver function tests be performed before the initiation of treatment, and thereafter when clinically indicated.

Simvastatin occasionally causes myopathy manifested as muscle pain, tenderness or weakness with creatine kinase above 10 x ULN. Myopathy sometimes takes the form of rhabdomyolysis with or without acute renal failure secondary to myoglobinuria, and rare fatalities have occurred. Predisposing factors for myopathy include advanced age (≥ 65 years), female gender, uncontrolled hypothyroidism, and renal impairment. The risk of myopathy, including rhabdomyolysis, is dose related. The risk of myopathy and rhabdomyolysis is increased by high levels of statin activity in plasma. Simvastatin is metabolized by the cytochrome P450 isoform 3A4 (CYP3A4). Certain drugs which inhibit this metabolic pathway can raise the plasma levels of simvastatin and may increase the risk of myopathy. These include itraconazole, ketoconazole, posaconazole, voriconazole, the macrolide antibiotics erythromycin and clarithromycin, and the ketolide antibiotic telithromycin, HIV protease inhibitors, boceprevir, telaprevir, the antidepressant nefazodone, cobicistat-containing products, or grapefruit products. Combination of these drugs with simvastatin is contraindicated. If short-term treatment with strong CYP3A4 inhibitors is unavoidable, therapy with simvastatin must be suspended during the course of treatment.

Increases in HbA1c and fasting serum glucose levels have been reported with HMG-CoA reductase inhibitors, including simvastatin.

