7.3 Evaluation During Study Intervention

7.3.1 Study Visit 2

Study Visit 2 will occur 3 months (\pm 1 month) after the initiation of the intervention. Participants will be told to fast for 8 hours before the study visit. Fasting instructions will be provided to participants prior to their study visit, and participants will receive a phone call reminder the day before the visit to fast overnight. The following procedures/evaluations will be performed during this visit:

1. Review medical history, medications, and laboratory test results
2. Physical exam including measurement of weight and symptom assessment
3. Vital signs assessment: blood pressure, heart rate, respiratory rate, and oral temperature
4. ECOG performance status
5. Pregnancy test for women of child-bearing potential. Women who have had a hysterectomy, both ovaries removed, or a tubal ligation will not be required to have a pregnancy test.
6. Blood collection for clinical labs (approximately 10 mL). Laboratory blood tests will be done for a Complete Blood Count and Automated Differential (CBDF), a Complete Metabolic Panel (CMPL), and a Lipid Panel to monitor for potential adverse effects of the intervention and to confirm that laboratory levels meet the eligibility requirements for continuation in the trial (See Appendix A). If lab results within 30 days prior to this visit for any of these tests are available in the medical record, the blood test(s) will not be done.
7. Blood collection for research purposes (26 mL): 6 mL will be collected for measurement of protocol-specific biomarkers (serum concentrations of cytokines, chemokines, and adhesion molecules), and 20 mL will be banked for DNA extraction and future studies.

8. Fecal specimen for measurement of fecal elastase. A stool collection kit and instructions will be provided to the participant before the scheduled visit. The specimen will be self-collected at home. The participant will receive a phone call reminder the day before the visit to collect the fecal specimen and bring it to the study visit.
9. Self-administered QLQ-C30 and QLQ-PAN28(CP) to assess quality of life and pain level
10. Review of conformance with inclusion /exclusion criteria
11. Collect study agent and diary
12. Assess compliance (pill count)
13. Review study diary
14. Assess adverse events
15. Dispense study agent and diary. Each participant will be given a 3-month supply of the study agent (1 bottle of 120 capsules).

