8.3 Off-Agent Criteria

Participants may stop taking study agent for the following reasons: completed the protocol-prescribed intervention, adverse event or serious adverse event, inadequate agent supply, noncompliance, concomitant medications, or medical contraindication. Participants who experience complications of pancreatitis or develop intercurrent pancreatitis during the study will be instructed to continue taking the study agent unless they are unable to take oral medications. The study agent will be resumed as soon as they are able to tolerate oral medications. Participants will continue to be followed, if possible, for safety reasons and in order to collect endpoint data according to the schedule of events.

As described in section 7.5, clinical research staff will make follow-up telephone calls to the participants on days 30 ± 7 , 60 ± 7 , and 90 ± 7 after the participant discontinues the study agent to assess symptoms and adverse events. Standard of care data (medical history, laboratory test results, concomitant medications, imaging results) will continue to be collected via review of the participant's electronic medical record at the time points specified in the Schedule of Time and Events. If feasible, we will conduct a research visit to collect final measurements for participants who permanently discontinue the study agent early. An end-of-study research visit will be conducted 6 months after initiation of the statin intervention (Study Visit 3). The blood collections for clinical labs and banked samples future research, and the follow-up risk questionnaire will not be done. The following procedures will be performed during the end-of-study visit:

1. Review medical history, medications, and laboratory test results
2. Vital signs assessment, measurement of weight, and symptom assessment
3. ECOG performance status

4. Pregnancy test for women of child-bearing potential. Women who have had a hysterectomy, both ovaries removed, or a tubal ligation will not be required to have a pregnancy test.

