8.4 Off-Study Criteria

Participants may go 'off-study' for the following reasons:

- Adverse Event
- Death
- Disease Progression
- Lost to follow-up/Participant Withdrawal
- Participant Refused Follow-up
- Physician Decision
- Protocol Defined Follow-up Completed
- Protocol Violation
- Study Complete
- Ineligible
- Other

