11.1.3 Severity of AEs

11.1.3.1 Identify the AE using the CTCAE version 4.0. The CTCAE provides descriptive terminology (MedDRA lowest level term) and a grading scale for each AE listed. A copy of the CTCAE can be found at http://ctep.cancer.gov/protocolDevelopment/electronic_applications/ctc.htm.

AEs will be assessed according to the grade associated with the CTCAE AE term. AEs that do not have a corresponding CTCAE term will be assessed according to the general guidelines for grading used in the CTCAE v4.0. as stated below.

CTCAE v4.0 general severity guidelines:

Grade	Severity	Description
1	Mild	Mild; asymptomatic or mild symptoms; clinical or diagnostic observations only; intervention not indicated.
2	Moderate	Moderate; minimal, local or noninvasive intervention indicated; limiting age-appropriate instrumental activities of daily living (ADL)*.
3	Severe	Severe or medically significant but not immediately life-threatening; hospitalization or prolongation of hospitalization indicated; disabling; limiting self-care ADL**.
4	Life-threatening	Life-threatening consequences; urgent intervention indicated.
5	Fatal	Death related to AE.

ADL

*Instrumental ADL refers to preparing meals, shopping for groceries or clothes, using the telephone, managing money, *etc.*

**Self-care ADL refers to bathing, dressing and undressing, feeding self, using the toilet, taking medications, and not bedridden.

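### Section 5.6 words restart as mandatory once a related severe event resolves, with no exception for grade 4 events, rhabdomyolysis or serious hypersensitivity, and no section says that the off-agent criteria qualify it

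*Combined protocol and SAP*

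**What the plan says.** Section 5.6 (Dose Modification) contains two restart rules.

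- **General rule.** The agent is stopped for an adverse event of grade 3 or higher judged possibly, probably or definitely related. Then: "The study agent will be restarted after resolution".
- **Muscle and liver rule.** The agent is paused for related myopathy of grade 1 or greater (unexplained muscle symptoms with CPK above 2.5 times ULN) or hepatotoxicity (ALT or AST above 1.5 times ULN). Tests are repeated at 4 weeks. Values still raised mean permanent discontinuation. Otherwise: "If the lab test results return to normal levels, participant will go back on the study agent".

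The only other stop in 5.6 is for starting a listed interacting drug. No dose modifications are planned, so a restart is at the full 40 mg.

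Section 8.3 (Off-Agent Criteria) permits stopping for an adverse event, a serious adverse event or a medical contraindication. It also provides for those who stop for good: "If feasible, we will conduct a research visit to collect final measurements for participants who permanently discontinue the study agent early". Section 8.4 (Off-Study Criteria) lists adverse events and "Physician Decision".

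**The concern.** Resolution, or a normal laboratory result, is the only condition on restart. How dangerous the event was plays no part. Section 11.1.3 describes grade 4 as "Life-threatening consequences; urgent intervention indicated", and grade 4 falls inside the general rule. Section 6.2 warns: "Myopathy sometimes takes the form of rhabdomyolysis with or without acute renal failure secondary to myoglobinuria, and rare fatalities have occurred". Yet the muscle rule has no upper limit of severity, so rhabdomyolysis whose laboratory values return to normal is covered by it.

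The entry criteria are stricter. Section 4.2.4 excludes anyone with a "History of adverse effects, intolerance, or allergic reactions attributed to compounds of similar chemical or biologic composition to simvastatin". A reaction to a related drug bars entry, while a resolved severe reaction to simvastatin itself is followed, on the wording of 5.6, by re-exposure.

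What is at stake is participant safety and consistent handling across four sites. A site that relies on 5.6 would restart. A site that relies on 8.3 would not. The protocol does not say which is right.

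**Working it through.** No sample size, power or alpha figure is involved, so the check is a comparison of texts: does any section create an exception to the restart sentences, or say which text prevails?

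1. **Limits inside 5.6.** There are two: laboratory values still raised at 4 weeks, and a new interacting drug. Neither depends on grade or type of event. Severe muscle injury that clears within 4 weeks passes the first limit. A resolved allergic reaction has no laboratory test to pass and falls under the general rule if it was grade 3 or higher.
2. **Section 8.3.** It is permissive and covers the right reasons. Its section cross-reference is to 7.5 (follow-up calls), not to 5.6.
3. **Section 8.4.** This is a bare list of reasons for leaving the study, which is a different matter from staying in follow-up off drug. It does not mention 5.6.
4. **Sections 11.2.1 to 11.2.3.** A life-threatening event is an SAE. It is phoned to the Medical Monitor within 24 hours of the site learning of it and, if related, followed until resolved. Restart comes only after resolution, so the call would normally come first. The text sets a reporting duty and says nothing about who decides on restart.
5. **Section 12.4.** The Data Monitoring Committee reviews SAEs and also protocol deviations. Nothing says whether withholding drug against the wording of 5.6 counts as a deviation.
6. **Section 7.3.1, Study Visit 2.** The visit includes "Review of conformance with inclusion /exclusion criteria" before the second bottle is dispensed. This is partial cover. It happens once, at about Month 3, while a restart can fall between visits, and 4.2.4 is worded for other statins.

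Result: several sections give a way to keep the participant off drug. None creates an exception to the restart sentences or ranks itself above them.

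**On frequency.** The nearest figure is in section 2.2: myopathy in about 0.08% of patients at 40 mg. For 20 simvastatin participants that is 20 × 0.0008 = 0.016 expected cases of any myopathy. This supports calling such events rare, and no more. The figure comes from a database in which 60% of patients were in studies with median follow-up of at least 4 years, against 6 months here. Section 2.2 does not define myopathy, so the figure cannot be matched to the trigger in 5.6. It also says nothing about how often a severe case resolves and is restarted. No rate is given for related grade 4 events or serious hypersensitivity.

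**The case against.** The strongest reply is that 5.6 states the default and 8.3 the reasons to depart from it, so that only a cross-reference is missing. The safeguards around it are real. The Medical Monitor would normally hear of these events before a restart could arise. Participants are told to call the study doctor at once about a serious reaction (5.4). Sites are pointed to the Investigator Brochure or package insert (section 11) and are bound by GCP (14.6). The muscle rule is itself cautious: it pauses drug at CPK above 2.5 times ULN, whereas 6.2 describes myopathy with creatine kinase above 10 times ULN. The hypersensitivity limb has thin support, since 6.2 lists rash but no anaphylaxis.

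Much of this stands. A reader might infer from 5.6 that the protocol compels re-challenge after a life-threatening reaction. The documents do not support that, because 8.3 and 8.4 allow the participant to be kept off drug.

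What does not fall away is the wording. A general permission to stop does not clearly displace a specific instruction to restart, and no section says that it does. Followed as written, 5.6 directs an unsafe re-exposure. That is a stated rule to correct rather than a missing detail.

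**Conclusion.** The point holds as a defect in the wording of 5.6 with a safety consequence, and correcting it is a cheap improvement. It rests on the text alone: two mandatory restart sentences, no exception for the gravest events, and no statement that 8.3 or 8.4 prevails.

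Its size is a rare event with serious consequences in each case. A reader might turn the 0.08% into a probability for this trial, or shorten it to 6 months and quote a range. Neither would be a floor or a ceiling for the case that matters, because the figure counts any myopathy rather than one that is severe, resolves and is restarted. No probability is therefore claimed.

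Nor do the documents support requiring monitor consultation for every resolved low-grade rise in CPK, ALT or AST. The existing 4-week rule is adequate for those.

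**What to change.** In section 5.6, replace the sentence "The study agent will be restarted after resolution" with:

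*Subject to 8.3, the study agent may be restarted after resolution at the investigator's discretion, in consultation with the medical monitor. It will not be restarted after a related grade 4 event, rhabdomyolysis, anaphylaxis, or a related hypersensitivity reaction of grade 3 or higher.*

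Keep the existing restart rule for low-grade myopathy and hepatotoxicity, and add to the end of that sentence only:

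*unless the event was grade 3 or higher or rhabdomyolysis, in which case the rule above applies.*

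The cost is a short amendment, which needs DCP and IRB approval under 14.3, and a monitor consultation confined to the more serious related events. Rarely, a participant will be kept off drug. That participant stays in the assigned group under the intention-to-treat rule in 13.5, and 8.3 already provides a Month-6 ePFT if feasible, so the primary endpoint need not be lost.

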4. PARTICIPANT SELECTION

4.1 Inclusion Criteria

4.1.1 At least two episodes of acute pancreatitis in the past 12 months. Acute pancreatitis is defined as any 2 of the following: (1) Typical upper abdominal pain; (2) Elevation in serum amylase or lipase ≥ 3 times upper limit of normal; (3) Features of acute pancreatitis on cross-sectional imaging.

4.1.2 Age ≥ 18 years.

4.1.3 ECOG performance status ≤ 1 (Karnofsky $\geq 70\%$; see Appendix B).

4.1.4 Participants must have acceptable organ, hepatic and renal function as defined below:

Leukocytes	$\geq 2,500/\text{microliter}$
Absolute neutrophil count	$\geq 1,500/\text{microliter}$
Platelets	$\geq 100,000/\text{microliter}$
Hemoglobin	$> 10 \text{ g/dL}$
Total bilirubin	$\leq 3 \times$ institutional upper limit of normal (ULN)
AST (SGOT)/ALT (SGPT)	$\leq 1.5 \times$ institutional ULN
Creatinine	$< 1.5 \text{ mg/dL}$

Patients whose lab levels meet the inclusion criteria by Screen 2 will be included in the trial.

4.1.5 Women of child-bearing potential must have a confirmed negative pregnancy test result prior to enrollment.

4.1.6 The effects of simvastatin on the developing human fetus at the recommended therapeutic dose are unknown. For this reason and because statins are known to be teratogenic, women of child-bearing potential must agree to use adequate contraception (hormonal or barrier method of birth control; abstinence) prior to study entry and for the duration of study participation. Should a woman become pregnant or suspect she is pregnant while participating in this study, she should inform her study physician immediately. It is not known whether simvastatin is excreted into human milk; however, a small amount of another drug in this class does pass into breast milk. Because statins have the potential for serious adverse reactions in nursing infants, women who receive treatment with simvastatin should not breastfeed their infants.

4.1.7 Ability to understand and the willingness to sign a written informed consent document and medical release.

4.1.8 Willing and able to comply with trial protocol and follow-up.

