7.3.2 Telephone Calls and Email/Text Messages

Study participants will be followed during intervention via telephone calls every four weeks (± 7 days) by the clinical research staff to assess compliance and adverse events. Participants who report having taken $< 80\%$ of the study drug doses between phone calls, or whose pill count at a study visit reveals $< 80\%$ compliance, will be called every two weeks (± 3 days) to monitor compliance. In addition, participants will receive a phone call the day before each scheduled study visit to remind them to fast overnight and to collect a fecal specimen and bring it to the study visit. Participants will also be reminded to bring any leftover study drugs and the study diary with them to the visit. Study participants will also be called during the week before their final visit (Visit 3) to remind them to take the study drug every day until the visit appointment.

Participants who opt to receive reminders for study medication intake via email or text messages will be contacted by the study staff during the first week of study and further as needed. The study staff will send emails or text messages on cellular phone; participants will be encouraged to respond to these messages indicating if the study drug has been taken. These responses will be used to assess compliance and will be reviewed at weekly phone contact. For participants who miss more than one dose in a week, the email/text reminders will continue further into dosing period. Since agent compliance is very important during the final week of the intervention, text/email messages will be sent to all study participants who opt to receive these reminders.

The following information will be collected during the telephone calls:

1. Medication compliance review. Participants will be asked if they missed any doses of medication, and the dates of all missed doses will be recorded.
2. Concomitant medication review
3. Adverse events. Participants will be asked if they have experienced any of the following symptoms to assess adverse events:
 - a. Upper respiratory infections
 - b. Headache
 - c. Abdominal pain
 - d. Constipation
 - e. Nausea / Vomiting

4. Additional symptoms experienced by participants will be recorded to assess adverse events

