APPENDIX C

Study Diary

Statin Therapy to Reduce the Risk of Recurrent Pancreatitis

Please bring your completed diary and your study drug supply, including empty bottles, with you to every study visit. This will help us keep track of your study drug and how well you are tolerating it.

Protocol Number: NWU2014-04-01 **Site:** _____
Participant Study ID: _____ **Participant Name:** _____
Date Study Drug Dispensed: _____ **Participant Signature:** _____

Instructions

Complete one line in the table for each day you take the study drug.

- Take your study drug once per day at bedtime or with an evening meal. Take the capsule at the same time every day. Please swallow the capsule whole and do not chew, crush, or open it.
- Record the date and time of day you took the study drug.
- If you notice any side effects such as headache, abdominal pain, constipation, nausea or vomiting, respiratory infection, or mild skin rash, or if you have any comments please record them in the Side Effects/Comments column and tell the study staff when they call you.
- If you miss a dose of the study drug, take it as soon as you remember. Do not take the drug if it has been more than 12 hours since you missed your last dose. Wait and take the next dose at your regular time. Do not take 2 doses of the study drug at the same time. Please write the reason for missing a dose in the Side Effects/Comments column.
- Using this pain scale, write a number for the amount of pain you feel **today** in the Pain Level column.

0	1	2	3	4	5
No pain	Very mild pain	Mild pain	Moderate pain	Severe pain	Very severe pain

Day	Date	Time Study Drug Taken	Pain Level	Side Effects/Comments
1		____:____  a.m. /  p.m.		
2		____:____  a.m. /  p.m.		
3		____:____  a.m. /  p.m.		
4		____:____  a.m. /  p.m.		
5		____:____  a.m. /  p.m.		
6		____:____  a.m. /  p.m.		
7		____:____  a.m. /  p.m.		
8		____:____  a.m. /  p.m.		
9		____:____  a.m. /  p.m.		
10		____:____  a.m. /  p.m.		

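### Section 5.6 restarts the study agent after a myopathy hold on blood tests alone, so a participant whose related muscle symptoms persist is put back on it

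*Combined protocol and SAP*

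**What the plan says.** Section 5.6 (Dose Modification) contains two separate stopping rules. The first stops the agent for any related adverse event of grade 3 or higher and allows restart once the event has resolved. The second covers milder muscle and liver toxicity. For muscle, the agent is held when the participant has unexplained muscle symptoms and, in addition, CPK above 2.5 times the institutional upper limit of normal (ULN), with at least a possible link to the agent.

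Three sentences then govern what follows a hold under the second rule:

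- How resolution is judged: "Resolution of myopathy or hepatotoxicity will be evaluated with follow-up laboratory blood tests 4 weeks after the elevated levels occur".
- When to stop for good: "If the lab test results are still elevated after 4 weeks, the study agent will be discontinued permanently".
- When to restart: "If the lab test results return to normal levels, participant will go back on the study agent".

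Earlier in the same paragraph, statin myopathy is described as "muscle weakness or other muscle injury with or without elevation in CPK level". It is distinguished there from myalgia, meaning muscle pain with a normal CPK, which is called a common side effect and does not by itself lead to a hold.

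**The concern.** Two findings are needed to declare the event, but only one of them is checked to declare it over. A participant can have a related myopathy confirmed by CPK, return at 4 weeks with a normal CPK and muscle weakness or pain still present, and be restarted as the protocol directs. On the protocol's own description a normal CPK does not show that a myopathy has gone. What is at stake is avoidable re-exposure of someone who has already had a drug-related muscle event and still has symptoms of it.

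**Working it through.** No sample-size, power or alpha figure bears on this point. The check compares the rules, then bounds how often they could matter.

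**Hold rule against restart rule (section 5.6)**

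| | Muscle symptoms | CPK |
|---|---|---|
| Hold | required | above 2.5 × ULN required |
| Judging resolution at 4 weeks | not mentioned | blood test |
| Restart | not mentioned | back to normal |
| Permanent stop | not mentioned | still raised |

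A participant with a normal CPK and persisting symptoms below grade 3 falls in the restart row. The grade 3 rule does not reach that participant.

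**Whether another section closes the gap**

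- 8.3 (Off-Agent Criteria): "Participants may stop taking study agent for the following reasons", and an adverse event is among the reasons listed. The wording permits stopping; it sets no condition for restart.
- 8.4 (Off-Study Criteria): an adverse event and a physician's decision are listed as reasons to leave the study. These too are optional and say nothing about restart.
- 5.4 (Contraindications): promises close monitoring for symptoms, without tying it to a dosing decision.
- 11.1.5 (Follow-up of AEs): events are followed under good medical practice. No restart condition is set.
- 5.6 and 7.6: a report of muscle pain or weakness leads to a repeat CPK, which is the same laboratory value again.

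None of these adds a symptom condition.

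**How many participants could be involved**

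Inputs: 20 participants on simvastatin (5.1); myopathy incidence of about 0.08% at 40 mg (2.2); a bound of under 1% for myopathy (5.6, 7.6).

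- At 0.08%: expected events = 20 × 0.0008 = 0.016; chance of at least one = 1 − 0.9992^20 = 1.6%.
- At the 1% bound: expected events below 20 × 0.01 = 0.2; chance of at least one below 1 − 0.99^20 = 18.2%.

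The 0.08% rate is a rough guide that could err either way. Section 6.2 describes myopathy with creatine kinase above 10 × ULN, which is 10 / 2.5 = 4 times the hold limit, so holds could be more frequent. Against that, section 2.2 says 60% of the patients in that database were in studies with a median follow-up of at least 4 years, compared with 6 months of dosing here.

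Both results count every myopathy. The affected group is smaller: held, CPK normal at 4 weeks, still symptomatic, and below grade 3. The documents give no rate for that group.

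**The case against.** The strongest reply is that restart mirrors hold. The trigger needs both symptoms and a raised CPK; once CPK is normal the trigger is no longer met, and what remains looks like myalgia, for which the plan holds nobody. On this view the remark that myopathy can occur without a CPK rise is background, and asking for more at restart than at hold is a preference. Part of this stands: the rule is consistent with its own two-part definition, and persisting mild pain is weaker evidence of continuing injury than persisting weakness. It does not remove the point. A participant who has just had a related myopathy confirmed by CPK and still has symptoms is in a different position from one with new isolated muscle pain, and the restart wording is a direction, not an option.

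The second reply is that nobody would be re-exposed unnoticed. A reader might infer from the symptom lists that muscle complaints go undetected: section 7.3.2 says "Participants will be asked if they have experienced any of the following symptoms to assess adverse events" and then names no muscle symptom, and the diary prompt in Appendix C reads "If you notice any side effects such as headache, abdominal pain, constipation, nausea or vomiting, respiratory infection, or mild skin rash". The documents do not support that inference. Calls take place every four weeks and additional symptoms are recorded; the diary list gives examples only; symptoms are assessed at Study Visits 2 and 3; item 42 of the QLQ-PAN28(CP) asks about weakness in the arms and legs; and section 11.1.2 requires an end date and outcome for each adverse event, so an unresolved one stays visible. The consent form is not in the text reviewed, so its instructions cannot be presumed silent. Symptoms would probably be known. The gap is that the rule gives them no part in the restart decision.

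A reader might also infer a second defect, that the terms for normal and still-raised results carry no number. Section 4.1.4, headed "Participants must have acceptable organ, hepatic and renal function as defined below", admits ALT or AST up to 1.5 × ULN, so a baseline slightly above ULN is possible. But 5.6 states its hold limits just before using these terms, the ALT/AST limit there is the same 1.5 × ULN, and section 7.3.1 checks continuing participants against the eligibility limits. Together these largely settle the liver reading. What remains is missing detail and is not part of this point.

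**Conclusion.** The point holds as a minor safety gap. Followed as written, section 5.6 returns a participant to the agent while symptoms of a related myopathy below grade 3 persist, and the provisions that could prevent it depend on an investigator's discretion against a directive sentence.

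The size is very small: 0.016 expected myopathies among 20 simvastatin participants at the 0.08% rate and under 0.2 at the stated bound, with only a fraction of those affected. This rests on the quoted rates applying to this population and on the planned 20 being treated.

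It would be wrong to infer damage to the primary comparison. No endpoint, power or alpha figure changes, and anyone held or restarted stays in the assigned group under the intention-to-treat rule in section 13.5.

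**What to change.** Keep the laboratory conditions in 5.6 as they stand and add a symptom condition to the restart sentence: *for a participant held for myopathy, restart also requires that the unexplained muscle symptoms have resolved on direct questioning at the 4-week check; if symptoms persist with normal laboratory results, the hold continues until they resolve.* Record the answer at that check. Leave the grade 3 rule unchanged.

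Two other remedies are less suitable. Setting the CPK condition for restart at the 2.5 × ULN hold limit would relax the present requirement: a symptom-free participant at 2.4 × ULN would restart. Requiring permanent discontinuation for any lingering symptom at a single check would be a debatable trade-off, because mild pain with normal CPK is not otherwise a reason to stop.

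The cost is one sentence and one question at a recheck that already takes place, with no new tests. The downside is that a very small number of participants may stay off agent longer. As an illustration, take a hold that starts at Study Visit 2, assumed to be week 13 of 26. The 4-week check falls at week 17, so at most 26 − 17 = 9 further weeks are at issue, or 9/26 = 35% of planned dosing. An earlier hold could cost more, a later one less.
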